6.1.2 Immunogenicity endpoints

For immunogenicity endpoints, primary analyses of primary endpoints (including non-inferior hypotheses) are conducted in the evaluable immunogenicity populations. Secondary analysis will also be performed in the expanded population.

6.1.2.1 S and S-RBD binding IgG levels

- Estimands: geometric mean value
- Analysis set: 1/2/3-dose evaluable and expanded immunogenicity populations
- Time points: before dose 1, before dose 2, 1 month after dose 2, 2 weeks after dose 3, 6, 18 and 36 months after vaccination
- Statistics: Geometric mean; % with value above LLOD
- Figure: column scatter dot plot with geometric mean and CI95 error bars
- Intercurrent events: Values below the LLOD will be set to 0.5 of the cut-off/limit for analysis.

6.1.2.2 Surrogate neutralizing antibody inhibition levels

- Estimands: geometric mean value
- Analysis set: 1/2/3-dose evaluable and expanded immunogenicity populations
- Time points: before dose 1, before dose 2, 1 month after dose 2, 2 weeks after dose 3, 6, 18 and 36 months after vaccination
- Statistics: Geometric mean; % with value above LLOQ
- Figure: column scatter dot plot with geometric mean and CI95 error bars
- Intercurrent events: Values below the LLOQ will be set to 0.5 of the cut-off/limit for analysis.

6.1.2.3 Neutralizing antibody titers

- Estimands: geometric mean value
- Analysis set: 1/2/3-dose evaluable and expanded immunogenicity populations
- Time points: before dose 1, before dose 2, 1 month after dose 2, 2 weeks after dose 3, 6, 18 and 36 months after vaccination
- Statistics: Geometric mean; % with value above LLOD
- Figure: column scatter dot plot with geometric mean and CI95 error bars
- Intercurrent events: Values below the LLOD will be set to 0.5 of the cut-off/limit for analysis.

6.1.2.4 S binding IgG avidity index

- Estimands: geometric mean value
- Analysis set: 1/2/3-dose evaluable and expanded immunogenicity populations
- Time points: before dose 1, before dose 2, 1 month after dose 2, 2 weeks after dose 3, 6, 18 and 36 months after vaccination
- Statistics: Geometric mean
- Figure: column scatter dot plot with geometric mean and CI95 error bars
- Intercurrent events: N/A.

6.1.2.5 Anti-S FcgRIIIa-binding IgG levels

- Estimands: geometric mean value
- Analysis set: 1/2/3-dose evaluable and expanded immunogenicity populations
- Time points: before dose 1, before dose 2, 1 month after dose 2, 2 weeks after dose 3, 6, 18 and 36 months after vaccination
- Statistics: Geometric mean; % with value above LLOD
- Figure: column scatter dot plot with geometric mean and CI95 error bars
- Intercurrent events: Values below the LLOD will be set to 0.5 of the cut-off/limit for analysis.

6.1.2.6 S (and N and M)-responsive Th1 and Tc1 cell frequencies

- Estimands: geometric mean frequency, geometric mean fold rise
- Analysis set: 1/2/3-dose evaluable and expanded immunogenicity populations
- Time points: before dose 1, before dose 2, 1 month after dose 2, 2 weeks after dose 3, 6, 18 and 36 months after vaccination
- Statistics: Geometric mean; % with value above cut-off
- Figure: column scatter dot plot with geometric mean and CI95 error bars
- Intercurrent events: Values below cut-off will be set to 0.5 of cut-off/limit for analysis

6.1.2.7 GMR of S and S-RBD binding IgG, surrogate neutralizing antibody inhibition level, neutralizing antibody titers, IgG avidity index and FcgRIIIa-binding IgG in participants 11-17 years of age to those 18 years of age or above

- Estimands: geometric mean ratios
- Analysis set: 1/2/3-dose evaluable and expanded immunogenicity populations
- Time points: 1 month after doses 1 and 2, 2 weeks after dose 3, 6, 18 and 36 months after vaccination; including cross-comparison of 1 month after dose 1 in adolescents and 1 month after dose 2 in adults (and 2 weeks after dose 3 in adults and 1 month after dose 2 in adolescents receiving SinoVac)
- Statistics: exponentiated difference in mean and CI95 on natural log scale for geometric means and two-sided CI95 (or one-sided CI97.5). For testing non-inferiority (one month after dose 2)

- Figure: forest plot
- Intercurrent events: Values below the cut-off/lower limit of detection/quantification may be set to 0.5 of the cut-off/limit for analysis if applicable for the assay.

6.1.2.8 GMR of S (and N and M)-responsive Th1 and Tc1 cell frequencies in participants 11-17 years of age to those 18 years of age or above

- Estimands: geometric mean ratio
- Analysis set: 1/2/3-dose evaluable and expanded immunogenicity populations
- Time points: 1 month after doses 1 and 2, 2 weeks after dose 3, 6, 18 and 36 months after vaccination
- Statistics: exponentiated difference in mean and CI95 on natural log scale for geometric means and two-sided CI95 (or one-sided CI97.5). For testing non-inferiority (one month after dose 2)
- Figure: forest plot
- Intercurrent events: Values below the cut-off/lower limit of detection/quantification may be set to 0.5 of the cut-off/limit for analysis if applicable for the assay.

6.1.2.9 GMR of S and S-RBD binding IgG, surrogate neutralizing antibody inhibition level, and neutralizing antibody titers, IgG avidity index and FcγRIIIa-binding IgG in participants 11-17 years of age receiving 2 doses of BNT162b2 to those receiving 2/3 doses of CoronaVac

- Estimands: geometric mean ratio
- Analysis set: 2/3-dose evaluable and expanded immunogenicity populations
- Time points: 1 month after dose 2, 2 weeks after dose 3, 6, 18 and 36 months after vaccination; including cross-comparison of two doses of BNT162b2 and three doses of CoronaVac
- Statistics: exponentiated difference in mean and CI95 on natural log scale for geometric means and two-sided CI95 (or one-sided CI97.5).
- Figure: forest plot
- Intercurrent events: Values below the cut-off/lower limit of detection/quantification may be set to 0.5 of the cut-off/limit for analysis if applicable for the assay.

6.1.2.10 GMR of total S responsive Th1 and Tc1 cell frequencies in participants 11-17 years of age receiving 2 doses of BNT162b2 to those receiving 2/3 doses of CoronaVac

- Estimands: geometric mean ratio
- Analysis set: 2/3-dose evaluable and expanded immunogenicity populations
- Time points: 1 month after dose 2, 2 weeks after dose 3, 6, 18 and 36 months after vaccination; including cross-comparison of two doses of BNT162b2 and three doses of CoronaVac

- Statistics: exponentiated difference in mean and CI95 on natural log scale for geometric means and two-sided CI95 (or one-sided CI97.5).
- Figure: forest plot
- Intercurrent events: Values below the cut-off/lower limit of detection/quantification may be set to 0.5 of the cut-off/limit for analysis if applicable for the assay.

6.1.2.11 GMR of S and S-RBD binding IgG, surrogate neutralizing antibody inhibition level, and neutralizing antibody titers, IgG avidity index and FcgRIIIa-binding IgG in participants receiving intradermal CoronaVac to intramuscular CoronaVac

- Estimands: geometric mean ratio
- Analysis set: 2/3-dose evaluable and expanded immunogenicity populations
- Time points: 1 month after dose 2, pre-dose 3, 2 weeks after dose 3, 6, 18 and 36 months after vaccination
- Statistics: exponentiated difference in mean and CI95 on natural log scale for geometric means and two-sided CI95 (or one-sided CI97.5).
- Figure: forest plot
- Intercurrent events: Values below the cut-off/lower limit of detection/quantification may be set to 0.5 of the cut-off/limit for analysis if applicable for the assay.

6.1.2.12 GMR of total S, N and M responsive Th1 and Tc1 cell frequencies in participants 11-17 years of age receiving intradermal CoronaVac to intramuscular CoronaVac

- Estimands: geometric mean ratio
- Analysis set: 2/3-dose evaluable and expanded immunogenicity populations
- Time points: 1 month after dose 2, pre-dose 3, 2 weeks after dose 3, 6, 18 and 36 months after vaccination
- Statistics: exponentiated difference in mean and CI95 on natural log scale for geometric means and two-sided CI95 (or one-sided CI97.5).
- Figure: forest plot
- Intercurrent events: Values below the cut-off/lower limit of detection/quantification may be set to 0.5 of the cut-off/limit for analysis if applicable for the assay.

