2.2 Study Design

2.2.1 Healthy adolescents

This is a single-center, immunobridging study in 200 healthy adolescents aged 11-17 years and their parents or other adult controls, in which participants elect to be immunized against COVID-19 with BioNTech BNT162b2 or SinoVac's CoronaVac. A variety of immunogenicity outcomes will be measured and bridged to their healthy parents to demonstrate respective non-inferiority of the vaccines in adolescents to adults. Reactogenicity and safety will also be described. Participants will be followed-up for a period of 3 years.

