3.3 Participant characteristics

Demographic variables obtained include age at time of dose 1 (in years), sex (male or female), medical history (generally healthy, pre-existing COVID-19 or immunodeficient), pre-existing conditions (coded according to medDRA) and concomitant medications.

4 Analysis sets

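### The vaccine and adolescent-adult geometric mean ratios are crude in a non-randomised design, although age, sex and sampling day could be adjusted for; the size of any bias is unknown

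*SAP*

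**What the plan says.** SAP 6.1.2.7 to 6.1.2.10 and 6.2.4 all give the same statistic for comparing groups: "exponentiated difference in mean and CI95 on natural log scale for geometric means and two-sided CI95 (or one-sided CI97.5". The general method in 5.2.2.3 adds no covariate, weight, pairing or cluster term.

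Section 2.2.1 describes a study "in which participants elect to be immunized against COVID-19" with one of two vaccines. The population is "200 healthy adolescents aged 11-17 years and their parents or other adult controls", and outcomes are to be "bridged to their healthy parents to demonstrate respective non-inferiority of the vaccines in adolescents to adults". The share of adult controls who are parents is not given.

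Section 3.3 records "age at time of dose 1 (in years), sex (male or female"), among other variables. Section 4.2 sets the evaluable sampling window at days 14-42 after dose 2 and days 13-42 after dose 3. The vaccine comparison is made at matching time points and also across regimens, "including cross-comparison of two doses of BNT162b2 and three doses of CoronaVac". Sections 6.1.2.7 and 6.2.4 likewise set adolescents one month after dose 2 against adults two weeks after dose 3.

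The only covariate model is in 3.2.4. It is an exploratory multiple regression on variables such as age, sex and haematological parameters, run separately by vaccine type and age subgroup. Sampling day is not among the variables it names.

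**The concern.** Two families of comparison carry the primary objectives in 2.1: vaccine against vaccine in the young, and adolescents against adults with a 0.6 margin. Neither is protected by randomisation.

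In the first, adolescents or their families choose the vaccine, so age, sex or other factors related to response may differ between the groups. In the second, the two groups have the same vaccine but may differ in sex mix and in mean sampling day. Any such difference enters the crude ratio directly. The regression in 3.2.4 cannot help, because a model fitted within one vaccine and one age group contains no contrast between vaccines or between age groups.

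At stake are a non-inferiority decision that could be wrong in either direction and a vaccine ratio whose interval is centred in the wrong place. Separately, an analysis that treats an adolescent and that adolescent's parent as independent does not use the correlation between them.

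**Working it through.** **Inputs from the SAP.** Margin 0.6, so ln(0.6) = -0.511 (5.1.1). SD 0.65 on the natural log scale; 61 per group for 99% power; 66 and 16 for 80% power in the plaque reduction neutralization test (PRNT) (5.1.2). Two-sided 95% intervals (5.2).

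**Assumed, because the SAP gives no figure.** Strength and imbalance of confounders, antibody half-life, gap in mean sampling day, and parent-child correlation.

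1. *The plan's own figures.* For 61 per group, SE = 0.65 × √(2/61) = 0.1177. Power = Φ(0.51/0.1177 - 1.96) = 99.1% (99.0% by noncentral t). For 66 and 16, SE = 0.65 × √(1/66 + 1/16) = 0.181 and power is 80.4% (79.4% by noncentral t). Both stated figures reproduce, on the basis of two independent, unbiased groups.

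2. *How large a bias could be.* A binary factor with effect F and a difference in prevalence of d multiplies the GMR by exp(d × ln F). For F from 1.25 to 2 and d from 0.10 to 0.30, this runs from exp(0.10 × ln 1.25) = 1.02 to exp(0.30 × ln 2) = 1.23. If one group is sampled 7 days later on average during decay, the multiplier is 2^(-7/half-life): 0.85 at 30 days and 0.95 at 90 days. If mean sampling days are equal, it is 1.

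3. *Effect on the 0.6 test, 61 per group.* The chance of declaring non-inferiority at a true GMR of 0.6 is 1 - Φ(1.96 - ln(bias)/0.1177).

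| Bias in favour of adolescents | ln(bias)/SE | False non-inferiority |
|---|---|---|
| none | 0 | 2.5% |
| 1.10 | 0.81 | 12.5% |
| 1.15 | 1.19 | 22.0% |

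In the other direction, a bias of 0.85 cuts power at a true GMR of 1 from 99.1% to Φ((ln 0.85 - ln 0.6)/0.1177 - 1.96) = 84.1%.

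4. *Effect on the vaccine ratio.* No margin applies here, so coverage is the measure. At a bias of 1.10, the nominal 95% interval covers Φ(1.96 - 0.81) - Φ(-1.96 - 0.81) = 87%. At 1.15 the same formula with 1.19 gives 78%.

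5. *Family links.* With a share f in parent-child pairs and correlation ρ, the correct SE is 0.65 × √((2/61)(1 - fρ)). At ρ = 0.2 with all in complete pairs, the planned interval is 1/√(1 - 0.2) = 1.12 times the correct width; with half in pairs, 1/√(1 - 0.1) = 1.05 times. For PRNT at most 16 one-to-one pairs exist, and the ratio is √[(1/66 + 1/16)/(1/66 + 1/16 - 0.4/66)] = 1.04. Over f = 0.5 to 1 and ρ = 0.1 to 0.5, true coverage is 95.6% to 99.4% and one-sided error is 0.022 to 0.003, below 0.025 throughout.

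6. *Cross-comparisons.* If samples cluster at two weeks and at one month, the gap is about 14 days. With decay half-lives of 30 to 60 days, that is a factor of 2^(14/30) = 1.38 to 2^(14/60) = 1.18. The windows in 4.2 are almost the same, so the actual gap may be smaller, and titres may still be rising at two weeks.

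**The case against.** The strongest reply is that nothing here shows a bias. The SAP gives no sign that the vaccine groups differ in age, that adolescents and adults differ in sex mix, or that their sampling days differ. Evaluable samples are restricted by window, and 6.4.2.2 and 6.4.3.1 report sampling and dosing in and out of window. A crude ratio at a named time point is a clear estimand. This stands as a limit on size: the percentages above say what a given bias would do, not that it is present. It does not justify leaving recorded variables unused in a self-selected comparison.

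A reader might go further in four ways that the document does not support.

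- *That every GMR has every one of these problems.* Self-election is the contrast only in 6.1.2.9 and 6.1.2.10. Parents enter only the adolescent-adult ratios. The SAP does not say how the intradermal or intramuscular route was assigned.
- *That ignoring family links gives intervals that are too narrow.* With a positive parent-child correlation they are too wide. The SAP does not mention siblings, and it allows other adult controls without giving their share.
- *That the 28-day window is itself a bias.* It adds variance. It shifts a ratio only if mean sampling days differ between the groups.
- *That adjusting for sampling day would repair the two-week versus one-month comparisons.* If the samples do cluster there, day nearly coincides with group, and the estimate would rest on an assumed common slope.

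**Conclusion.** The point holds for the vaccine comparisons (6.1.2.9, 6.1.2.10) and the adolescent-adult comparisons (6.1.2.7, 6.1.2.8, 6.2.4). Followed as written, the SAP yields unadjusted ratios for primary objectives in a non-randomised study, and the exploratory regression adjusts none of them.

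The rise in false non-inferiority from 2.5% to about 12-22% rests on the SAP's SD and group size and on an assumed bias of 1.10 to 1.15 in favour of adolescents. The actual size and direction are unknown. The sample-size figures are not in error. Adjustment is a better method at low cost; the crude plan is not shown to give a wrong answer. The family term is a matter of precision and corrects no inflated error rate.

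**What to change.** In 5.2.2.3, define the GMR for these comparisons as the exponentiated group coefficient from a pre-specified linear model of the natural log result on group, sex and days from last dose to sampling. For the vaccine comparisons within ages 11-17, add age at dose 1. Age is the contrast itself in the adolescent-adult ratios and should not be a covariate there. Keep the unadjusted ratio as a supportive analysis.

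Where adolescents' own parents are among the adults, add a random family intercept or a cluster-robust variance.

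For the comparisons of one month after dose 2 with two weeks after dose 3, report the distribution of sampling days in each group. State that timing partly coincides with group, and do not rely on the model to remove it.

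The cost is SAP wording and modest programming, with no new data. The model has to be fixed in advance, and it adjusts only for what is measured; confounding by unrecorded reasons for vaccine choice would remain and should be stated as a limitation.

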6.2 Secondary endpoints

6.2.1 Adverse events

We analyze unsolicited adverse events based on the following:

- Estimand: Percentage of participants reporting an adverse event (by medDRA terms)
- Analysis set: (healthy) safety population

- Time-point: after each dose on days 0-28, before the next dose
- Statistics: incidence (events per person), n and N

6.2.2 Vaccine efficacy prediction

We predict vaccine efficacy for adolescents in each vaccine based on neutralizing antibody correlate of protection, as published by Khoury et al in Nature Medicine, 2021. Geometric mean neutralizing titers in adolescents/children receiving either vaccines will be normalized against that of a set of house convalescent controls as fold of convalescent titers, and protective efficacy against symptomatic disease for either vaccine in adolescents/children by whichever route will be predicted based on the published model.

- Estimands: predicted protective efficacy (against symptomatic disease)
- Analysis set: 1/2/3-dose evaluable immunogenicity populations
- Time points: 1 month after dose 1/2 and 2 weeks after dose 3
- Statistics: Range of prediction will be given by CI95 of GMT and of model estimates.

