3.2.2 Vaccine efficacy prediction

We predict vaccine efficacy for recipients of each vaccine based on neutralizing antibody correlate of protection, as published by Khoury et al in Nature Medicine, 2021. Geometric mean neutralizing titers in participants receiving either vaccines will be normalized against that of a set of house convalescent controls as fold of convalescent titers, and protective efficacy against symptomatic disease will be predicted based on the published model.

3.2.3 anti-N and N-CTD IgG levels

We measure SARS-CoV2 full N and N-CTD binding antibody levels in sera as a primary immunogenicity endpoint. We report results as OD450 value. Values below the limit of detection will be taken as 0.5 of the lower limit of detection. Geometric mean OD450 values will be calculated for each timepoint in each subgroup.

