5.1.2 Sample size

When comparing the peak GM immunogenicity outcomes of children with that of adults, or between vaccine types, a sample size of 61 in each group would assure that a two-sided test with $\alpha=0.05$ has 99% power to detect an effect size with a Cohen's d value=0.78, corresponding to 1.67-fold difference on the linear scale, or 0.51 after natural log transformation, between 2 groups and a standard deviation (SD) of 0.65 on the natural log scale within each group. For assays with higher technical requirements such as PRNT, 66 evaluable adolescents/children and 16 evaluable adults tested would achieve 80% power to detect the same non-inferiority margin with the same α and SD; lower sample sizes may be applied on practical grounds. The statistical assumptions on effect size referred to the trial design and results by French et al in NEJM (2021) which found a GMR of 1.76 (95% CI 1.47-2.10) for PRNT50 in adolescents to young adults after 2 doses of BNT162b2. For the proportion of participants with a positive result in immunogenicity outcomes or ARs, 110 adolescents would yield a 95% chance to detect the true value within 7.5% of the measured percentage, assuming a prevalence of 80%. Recruitment of 120 participants were targeted per vaccine regimen and age group to accommodate for attrition.

Reference: French RW et al. Safety, Immunogenicity, and Efficacy of the BNT162b2 Covid-19 Vaccine in Adolescents. N Engl J Med (2021); 385:239-250.

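### The range for predicted vaccine efficacy leaves the convalescent mean's sampling error out of its titre component, and its overall coverage is unknown

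*SAP*

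**What the plan says.** SAP sections 3.2.2 and 6.2.2 describe the same prediction. Vaccinees' geometric mean neutralizing titres are to be "normalized against that of a set of house convalescent controls as fold of convalescent titers" (6.2.2), and efficacy against symptomatic disease "will be predicted based on the published model" (6.2.2). The model is external and the convalescent panel is the study laboratory's own.

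The only statement on uncertainty is in 6.2.2: "Range of prediction will be given by CI95 of GMT and of model estimates". It names two sources. The convalescent mean is not one of them, and the rule for combining the two is not given.

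Three other places bear on the reading:

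- Section 5.2.2.1 covers geometric means and their 95% intervals, with neutralizing titres as an example. Ratios of geometric means have their own section, 5.2.2.3.
- The between-group ratios in 6.1.2.7 to 6.1.2.12, 6.2.4, 6.2.6 and 6.2.7 are specified as exponentiated differences of log means with a 95% interval, which carries the variance of both groups.
- Section 3.1.2.3 measures both 50% and 90% neutralizing titres. Section 6.2.2 does not say which one enters the fold.

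**The concern.** The model input is a ratio of two estimated means from two independent sets of people. On the log scale its variance is the sum of the two variances. An interval built from the numerator alone is that of a different quantity. The interval of the published model cannot make up the difference, because an external model does not contain the sampling error of this laboratory's panel.

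At stake are the error bars on predicted efficacy, which is objective 16 and a secondary endpoint. The same panel divides every vaccine, dose, route and age group, so a chance error in its mean moves all absolute predictions in the same direction. Comparing the groups with one another would not reveal it.

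**Working it through.** **Inputs.** From section 5.1.2: "a standard deviation (SD) of 0.65 on the natural log scale within each group", and 66 adolescents or children with 16 adults for the plaque reduction neutralization test (PRNT). From sections 7.2 and 7.3: PRNT minima of 50 and 20 per vaccine. Assumed, because the SAP gives neither: the number of convalescent controls (20, 50 or 100) and their log SD (0.65, with 1.0 as a sensitivity value).

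**The plan's own figure first.** The SAP gives no number for the prediction range, but the SD and sample size used here can be checked against its PRNT power. SE of the difference = 0.65 × √(1/66 + 1/16) = 0.181. Then 0.51/0.181 − 1.96 = 0.86, which gives 80.4% power (79.0% with the t distribution). The stated 80% is reproduced.

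**Titre component.** With a the SE of the vaccinee log mean and c that of the convalescent log mean:

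- a = 0.65/√66 = 0.080. The interval multiplies and divides by exp(1.96 × 0.080) = 1.17.
- c = 0.65/√n = 0.145, 0.092 and 0.065 for n = 20, 50 and 100.
- SE of ln(fold) = √(a² + c²) = 0.166, 0.122 and 0.103.
- Coverage of the numerator-only interval for the fold = 2Φ(1.96·a/√(a² + c²)) − 1.

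| Assumed controls | Numerator only | Ratio interval | Log-scale width ratio | Coverage of numerator-only interval |
|---|---|---|---|---|
| 20 | ×/÷ 1.17 | ×/÷ 1.38 | 2.07 | 65.5% |
| 50 | ×/÷ 1.17 | ×/÷ 1.27 | 1.52 | 80.2% |
| 100 | ×/÷ 1.17 | ×/÷ 1.22 | 1.29 | 87.2% |

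With equal SDs the width ratio is √(1 + vaccinees/controls), for example √(1 + 66/20) = 2.07, so it does not depend on the value 0.65.

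**Sensitivity.** For 20, 50 and 100 controls the width ratio is:

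- 1.87, 1.41 and 1.22 with 50 vaccinees;
- 1.41, 1.18 and 1.10 with 20 vaccinees;
- 2.97, 2.03 and 1.60 with 66 vaccinees and a convalescent log SD of 1.0.

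**Whole range.** Let m be the model's SE in ln-titre units, with independent errors on a locally linear scale. The correct half-width is 1.96√(a² + c² + m²).

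- If the two named sources are combined in quadrature, the half-width is 1.96√(a² + m²), which is always too small.
- If lower limit is stacked on lower and upper on upper, it is 1.96(a + m). This reaches the correct width when 2am ≥ c², that is m ≥ c²/(2a) = 0.13, 0.053 and 0.026 for 20, 50 and 100 controls (66 vaccinees).

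**Efficacy scale, illustration only.** Assume a logistic curve, a point prediction of 70%, 66 vaccinees, 20 controls and no model error. The titre-driven range changes as follows:

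- slope 0.8 per ln unit: from 67.3–72.6% to 64.3–75.2%;
- slope 1.3: from 65.6–74.1% to 60.5–78.1%;
- slope 2.0: from 63.0–76.2% to 54.9–81.7%.

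The slopes are assumptions and are not taken from the published model.

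**The case against.** The strongest reply is that the reported range need not be too narrow. The SAP leaves the combination rule open, and stacking limits adds half-widths where quadrature would be correct, so it over-covers. With 66 vaccinees and 20 controls, a model SE of about 0.13 ln units would already offset the omission, and larger panels need less. This stands. A reader might infer from 6.2.2 that the whole range is too narrow, but the SAP does not support that. The shortfall is certain only for the titre component, and any offset would be accidental.

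A second reply is that the GMT in the rule may mean the normalized GMT, since the preceding text has just described the normalization, and the SAP handles ratios properly elsewhere. This is possible but unstated. Section 5.2.2 keeps geometric means and ratios apart, and 6.2.2 uses a different term for the normalized quantity, so someone programming from the text would compute the one-sample interval. A reader might also infer that the SAP declares the convalescent mean to be a known constant. It does not; it only fails to name that mean's error.

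Third, the sizes depend on a panel number and SD that the SAP does not give. That also stands. The panel may be described in the protocol, so its absence here is not a fault, and the figures remain illustrations. With few vaccinees and many controls the effect is small (1.10 for 20 and 100).

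Finally, the shared denominator cancels in titre ratios between vaccines, doses and ages, and the hypothesis tests in section 5.1.1 do not use the prediction. Both points are correct and limit the consequence to the absolute predictions.

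**Conclusion.** The point holds for the titre component. As written, it is the interval of a single mean applied to a ratio of two, and it is too narrow for any finite convalescent panel. With 66 vaccinees and a log SD of 0.65 assumed in both groups, its log-scale width should be 1.3 to 2.1 times as large for 100 down to 20 controls. The direction needs no assumption about the panel, but the size does.

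For the full range, the supportable conclusion is that its coverage is unknown: it may be too low or too high, depending on the combination rule and the model error. This warrants correction because a stated rule gives the wrong error bars and is easy to mend. It does not touch the primary analyses.

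**What to change.** In section 6.2.2, replace the interval of the GMT with the 95% interval of the fold. Compute ln(fold) = ln(GMT vaccinee) − ln(GMT convalescent), with variance equal to the sum of the two variances. Name the titre used (50% or 90%) and use the same one in both terms. State that this is combined with the model uncertainty in one joint propagation (delta method, bootstrap or Monte Carlo) to give a 95% range. Report the number of convalescent controls beside the prediction.

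The cost is a few lines of SAP text and a short calculation, with no further data from vaccinees. The downside is slightly more analysis work and a titre component that becomes wider.
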